4.0 Test Schedule

Tests and procedures	Active Monitoring Phase					
	Prior to registration		Prior to Day 1 Cycle 1	Prior to Day 1 Cycle 2	Prior to Day 1 Cycles 3-6	End of Treatment
	≤28 days	≤14 days				
Window				±3 days	±3 days	±7 days
Complete Medical History		X				
Physical exam, Wt, PS		X	X ³	X	X	X
Adverse event assessment		X		X	X	X
Pregnancy test ¹		X				
Height		X				
Hematology group: CBC with 5-part differential		X	X ³	X	X	X
Chemistry group to include serum creatinine, calcium, T.Bili, D. bili, AST, and ALT		X	X ³	X	X	X
LDH, Beta-2-microglobulin, Plasma cell assessment		X	X ³			
PT/PTT/INR		X				
TSH		X				
Electrophoresis of serum and urine		X	X ^{3,5}	X ⁵	X ⁵	X ⁵
Immunofixation or mass fixation of serum and urine		X		X ⁷	X ⁷	X ⁷
Affected Serum Immunoglobulin ²		X	X ³	X	X	X
Serum Immunoglobulin free light chain		X	X ³	X	X	X
WBLDCT ³ or PET/CT	X			X ³	X ³	
Bone marrow aspirate and biopsy	X					
Patient Medication Diary (Appendix II)			X	X	X	
Research bone marrow sample ^R	X			X ⁶		X ⁴
Research blood sample ^R	X			X ⁶		X ⁴

Cycle 1 = 21

Cycles 2-6 = 28 days

Footnotes on following page:

1. For women of childbearing potential only. Must be done ≤ 7 days prior to registration. If the urine test is positive or cannot be confirmed as negative, a serum pregnancy test will be required
2. Affected immunoglobulin refers to the baseline M-protein type, that is, IgG, IgA, or IgD. Not applicable if patient “non-secretory” or if patient has no heavy chain, i.e. light chain myeloma. Affected immunoglobulin is required after baseline only if it used for disease monitoring instead of SPEP (e.g. IgA myeloma).
3. Baseline then only if clinically indicated.
4. Optional BM sample submission for patients who discontinue treatment due to disease progression or relapse, intolerable AEs, patient refusal, subsequent treatment for myeloma.
5. Urine Electrophoresis required only if used to assess disease response
6. Bone marrow aspirate done at the end of Cycle 1 (prior to cycle 2) will be paid for by research.
7. Immunofixation (IF) only needed in absence of M-Spike to document CR or SCR

R Collected as part of the IRB# 521-93, IRB# 14-009163 and/or IRB# 919-04

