11.2 Confirmed response

In order to be classified as a hematologic response, confirmation of serum M- protein, serum immunoglobulin free light chain (when primary determinant of response) and urine M- protein (when primary determinant of response) results must be made by verification on two consecutive determinations.

- Bone marrow aspirate and biopsy are **only** required to document CR or sCR, except for patients with evaluable disease **only**, where a bone marrow is required to document all response categories including progression. However, a second confirmatory bone marrow is **not** required to confirm response in any case.
- Radiographic studies are not required to satisfy these response requirements; however, if radiographic studies were performed there should be no evidence of progressive or new bone lesions.

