Clinical Relapse	
One or more of the following direct indicators of increasing disease and/or end-organ dysfunction that are considered related to the underlying plasma cell proliferative disorder:
 
 1. Development of new soft tissue plasmacytomas or bone lesions on skeletal survey, magnetic resonance imaging, or other imaging 2. Definite increase in the size of existing plasmacytomas or bone lesions. A definite increase is defined as a 50% (and at least 1 cm) increase as measured serially by the sum of the products of the cross-diameters of the measurable lesion 3. Hypercalcemia ($>11.5 \text{ mg/dL}$; $>2.875 \text{ mM/L}$) 4. Decrease in hemoglobin of more than 2 g/dL (1.25 mM) or to less than 10 g/dL 5. Rise in serum creatinine by more than or equal to 2 mg/dL ($\geq 177 \text{ mM/L}$) 6. Hyperviscosity
------------------	---

^a All response categories require two consecutive assessments (sCR, CR, VGPR, PR, MR, PD) made at any time before the institution of any new therapy. sCR, CR, VGPR, PR, MR and SD categories require no known evidence of progressive or new bone lesions or extramedullary plasmacytomas if radiographic studies were performed. However, radiographic studies are not required to satisfy these response requirements. Bone marrow assessments need not be confirmed. Each category, except for stable disease, will have a working subcategory of "unconfirmed" [prefix 'u'] to designate first time point at which response category MAY have been achieved if confirmed. The date of the initial test is considered as the date of response for evaluation of time dependent outcomes such as duration of response.

^b CR patient will need to progress at the same level as VGPR and PR patients to be considered a PD. A positive immunofixation alone is not sufficient.

^c If more than one M protein spike meets the criteria for measurable disease at baseline, then both need to be followed for response. Otherwise, only follow the measurable M protein spike for response.

^d In patients in whom the only measurable disease is by serum FLC levels: CR in such patients indicates a normal FLC ratio of 0.26-1.65 in addition to the CR criteria listed above.

^e Bone marrow criteria for PD are only to be used in patients without measurable disease by M protein and by FLC;

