14.3 Metabolomics profiling

To determine if specific metabolite profiles within the bone marrow and peripheral blood plasma will be reflective of the metabolic phenotype within the clonal bone marrow plasma cells that predict for response to therapy with an IMiD.

Methodology: For this analysis, bone marrow and peripheral blood plasma will undergo large scale, untargeted metabolite profiling via liquid chromatography mass spectrometry. Differentially expressed metabolites in responder versus non-responders will be evaluated for the development of a potential biomarker predicting clinical response.

Sample type and timing: Bone marrow aspirate samples will be collected in (1) 5 ml EDTA (purple top) tube and placed on ice or a cool pack. Samples to be collected prior to cycle 1 and then prior to cycle 2.

Sample Destination:

[name]
Mayo Foundation
[name]
[name]

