14.4 Multiple myeloma cell retrieval

Samples type and timing: For studies utilizing intracellular metabolomics as well as genomics and transcriptomics of the MM cells, 35 ml of bone marrow aspirate will be obtained in (6) 6 mL ACD (yellow top) tubes in addition to the 5

ml of bone marrow aspirate from the (1) 5 mL EDTA (purple top) tube prior to cycle 1 and then prior to cycle 2.

Sample Destination:

[name]
Mayo Foundation
[name]
[name]

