16.0 Statistical Considerations and Methodology

16.1 Overview:

This is a pilot study to determine the response rates (>PR) of the combination of an immunomodulator and dexamethasone in Multiple Myeloma (MM) patients of each clinically relevant biomarker. This combination will be evaluated in four cohorts: Cohort A (Smoldering MM), Cohort B (Newly Diagnosed MM), Cohort C (Relapsed/Refractory MM) and Cohort D (Relapsed on Len maintenance). This study will not utilize a formal statistical design but will focus more on estimation rather than hypothesis testing.

16.11 Primary Endpoint: The primary endpoint of this trial is to estimate (>PR) response rates (RR) after one cycle of treatment. Biomarkers of interest will be identified and categorized into clinically relevant groups (e.g. positive vs. negative) by evaluating baseline and post treatment (after cycle one) biospecimens. RR will be estimated within each biomarker.

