16.2 Statistical Design

Due to the lack of data to identify relevant biomarkers, the estimation of RR would be of interest. In each group, the response rates will be examined to see if there's any preliminary evidence to suggest further studies. This study will not utilize a formal statistical design.

For each biomarker category, the RR will be estimated by the number of patients who achieve a PR or better divided by the total number of evaluable patients in each cohort. Exact binomial 95% confidence intervals for these rates will be calculated.

16.22 Sample Size: A maximum of 30 evaluable patients will be accrued in cohort A and B and 60 patients in cohort C and D respectively. We anticipate accruing an additional 2 in cohort A and B and 3 in cohort C and D to account for ineligibility, cancellation, major treatment violation, or other reasons. Therefore, the maximum projected accrual is 190 patients (A: 32, B: 32, C: 63 and D: 63).

16.23 Accrual Rate and Study Duration: The anticipated accrual rate is 6 evaluable patients per month. Therefore, the accrual period for this pilot study is expected to be approximately 32 months. The final analysis can begin approximately 35 months after the trial begins, i.e. as soon as the last patient has been observed for 1 months and allowing 2 months for data entry.

16.24 Other considerations: Adverse events, quality/duration of response, and patterns of treatment failure observed in this study, as well as scientific discoveries or changes in standard care will be taken into account in any decision to terminate the study

16.3 Analysis Plan.

The analysis for this study is planned to start after data maturity has occurred. It is anticipated that the earliest date in which the result will be available via manuscript, abstract or presentation after the last registered patient has been followed for at least 1 month.

16.31 Primary Outcome Analyses:

Each cohort (A-D) will be evaluated separately and independently.

16.311 Definition:

The primary endpoint of this study is RR after 1 cycle of treatment. RR is defined as a binary variable. A success will be defined as patient who achieve a response of a PR or better using the IMWG criteria (Section 11.0) after one cycle of treatment. All patients meeting eligibility criteria who have signed a consent form, who complete at least one cycle of treatment and have successfully submitted biospecimens (pre and post treatment) will be evaluable for the endpoint.

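### The biomarker groups used to estimate response rate may be set by the post-cycle-1 specimen; for markers that change with disease burden, such groups partly restate the response instead of predicting it

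*Combined protocol and SAP*

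**What the plan says.** Section 16.11 makes RR after one cycle the primary endpoint. It says biomarkers will be "categorized into clinically relevant groups (e.g. positive vs. negative) by evaluating baseline and post treatment (after cycle one) biospecimens", with RR estimated within each biomarker. It gives no rule for which specimen sets the category or how the two are combined, and 16.2 and 16.311 do not supply one.

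Section 16.311 counts as a success a patient who will "achieve a response of a PR or better using the IMWG criteria (Section 11.0) after one cycle of treatment". It makes a patient evaluable only if both the pre-treatment and the post-treatment specimen were submitted.

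The second specimen is placed in the prior-to-cycle-2 column of the Section 4.0 schedule (window ±3 days). Footnote 6 there reads "Bone marrow aspirate done at the end of Cycle 1 (prior to cycle 2) will be paid for by research". The same column holds the first scheduled on-treatment electrophoresis and free light chain tests.

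For metabolomics, Section 14.3 states "Samples to be collected prior to cycle 1 and then prior to cycle 2" and then "Differentially expressed metabolites in responder versus non-responders will be evaluated for the development of a potential biomarker predicting clinical response". It does not limit that comparison to the first sample. Section 14.4 takes marrow cells at the same two timepoints.

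Section 16.321 plans logistic regression to identify predictive biomarkers and names no timepoint. Section 16.323 separately relates biomarkers to depth of response.

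**The concern.** The stated purpose is prediction before treatment. Section 1.0 regrets that the effect of a therapy cannot be known until it has been given. Section 1.2 wants to recognise beforehand the patients who could be spared a third or fourth agent. Secondary goal 1 is to find biomarkers that predict response.

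A category fixed by the post-cycle-1 specimen is not known until the response is being measured. If the marker follows tumour burden, as a metabolite, transcript or plasma-cell measure may, a fall in burden moves both the marker and the response. A marker with no pre-treatment information can then show a clear RR contrast. The overlap is most direct where marrow is the only measurable disease, because Table 11.5 then defines partial response as a fall of at least 50% in marrow plasma cells.

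Section 16.2 examines the group rates for preliminary evidence to justify further studies, so a contrast of this kind could send the wrong marker forward.

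**Working it through.** **Plan's own figures.** Section 16.22 gives 30, 30, 60 and 60 evaluable patients in cohorts A to D. Accrual is 32 + 32 + 63 + 63 = 190, as stated. The plan gives no expected RR, marker correlation or cut-point, so all sizes below rest on assumed values.

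**Timing.** Baseline specimen: before cycle 1. Second specimen: end of cycle 1, before cycle 2. First scheduled on-treatment response tests: same schedule column. Endpoint: response after one cycle. A group that uses the second specimen is therefore concurrent with the outcome.

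**Step 1: expected contrast.** Let T be tumour reduction and M the post-cycle-1 marker, standard bivariate normal with correlation r. The marker's baseline value is independent of T. Response means T > c, with c = Φ⁻¹(1 − RR). Positive means M above its median. Each group's RR uses that group's own patients as denominator. Then

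- RR in positives = P(T > c, M > 0) / 0.5
- RR in negatives = [RR − P(T > c, M > 0)] / 0.5

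At RR = 0.40 and r = 0.5 the joint probability is 0.280. This gives 0.280/0.5 = 56% and (0.40 − 0.280)/0.5 = 24%.

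| Specimen setting the group | RR 30% | RR 40% | RR 50% |
|---|---|---|---|
| Baseline | 30/30 | 40/40 | 50/50 |
| Post-cycle-1, r = 0.1 | – | 43/37 | – |
| Post-cycle-1, r = 0.3 | 38/22 | 49/31 | 60/40 |
| Post-cycle-1, r = 0.5 | 44/16 | 56/24 | 67/33 |
| Post-cycle-1, r = 0.7 | 51/9 | 64/16 | 75/25 |

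**Step 2: how often a single cohort shows a gap.** With RR 40% and equal groups (15 + 15 or 30 + 30), sum two independent binomials over all outcomes whose rates differ by at least 20 points. Count either direction, because the plan specifies none.

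| Cohort size | Baseline | r = 0.1 | r = 0.3 | r = 0.5 | r = 0.7 |
|---|---|---|---|---|---|
| n = 30 | 35% | 38% | 57% | 82% | 97% |
| n = 60 | 15% | 19% | 52% | 88% | 99% |

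Chance alone gives a 20-point gap in about a third of cohorts of 30, so the baseline column is the fair comparator. At r = 0.1 little is added. At r = 0.3, Fisher's exact test reaches p < 0.05 in only 8.5% (n = 30) and 23% (n = 60).

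**Step 3: cross-check with another model.** The post-cycle-1 log marker equals its baseline value plus b times the log change in burden plus noise. Response is a burden fall of at least 50%. Standard deviations are 1 (baseline), 0.7 (burden change) and 0.3 (noise), with 4,000 simulated cohorts per setting. At n = 30:

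- Baseline groups: equal RR in every setting.
- Post-cycle-1 level: from 39 vs 21% (b = 0.5, RR 30%) to 68 vs 32% (b = 1, RR 50%).
- Change from baseline: from 52 vs 8% to 85 vs 15% in the same two settings.
- Marker unrelated to burden (b = 0): no contrast from any grouping.

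The direction agrees, and groups built on change are affected most.

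**The case against.** The best defence is that 16.11 says only that both specimens are evaluated. That can mean both are assayed, with the baseline value setting the group, and the rationale in 1.0 and 1.2 favours this. It stands as a possible reading, so a reader should not infer that the plan definitely groups patients by the second specimen. Still, 16.11 names both specimens in the sentence that forms the groups, and nothing in 14.3, 16.2, 16.311 or 16.321 restricts prediction to baseline. In goal 1, untreated describes the patients, not the specimen.

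A reader might also infer that every response is fixed at the moment of the second specimen. The documents do not support that. Section 11.2 says that "results must be made by verification on two consecutive determinations", so the confirming test may come later. The dating rule in Table 11.5, footnote a, concerns time-dependent outcomes such as duration of response and does not govern a binary RR. The overlap rests on biology and the shared visit window, not on that rule.

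Third, post-treatment values have a legitimate use. Agreed: 16.323 is a suitable home for them, but no text keeps that use apart from prediction.

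Finally, this is a declared pilot focused on estimation. That limits the consequence, but the bias would be in the very estimates used to decide on further studies.

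**Conclusion.** The point holds as an ambiguity with a real consequence under the literal reading. Nothing in the plan prevents a post-cycle-1 value from defining a group that is then reported as predicting response. For a burden-tracking marker with no baseline information, the spurious contrast is about 6 points at a correlation of 0.1 (43 − 37), 18 at 0.3 (49 − 31), 32 at 0.5 (56 − 24) and 48 at 0.7 (64 − 16), at an assumed RR of 40% with a median split. It is negligible at 0.1 and large from 0.5 upwards. The true correlations are unknown and will differ by marker.

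A reader might infer that all the biomarker results, or the primary RR itself, are compromised. They are not. Markers that treatment does not change are unaffected, such as stable genomic features among the studies in 14.4 ("For studies utilizing intracellular metabolomics as well as genomics and transcriptomics of the MM cells"). The overall RR in each cohort uses no biomarker grouping and is also unaffected. The wording should be settled before any response-by-marker results are seen.

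**What to change.** 1. In 16.11, 14.3 and 16.321, state that groups and models used to predict response are defined from the pre-cycle-1 specimen only.
2. In 16.323, state that post-cycle-1 values and changes from baseline are analysed separately, as pharmacodynamic correlates of response.
3. In 16.311, state whether the post-treatment specimen is still required for evaluability in the baseline-only analyses, or only for the pharmacodynamic ones.

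The cost is a few sentences, with no new patients, samples or tests. The downside is that some reported contrasts will be smaller, and post-cycle-1 findings can no longer be presented as predictors.

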7.0 Protocol Treatment

7.1 Treatment Schedule

Cohort A and B Cycle 1

Treatment medication table. Patient may receive Lenalidomide OR Lenalidomide + Dexamethasone.

Agent	Dose Level	Route	Day	Re Rx
Lenalidomide	25 mg*	Oral	Cycle 1: Day 1-14	Cycle 1: 21 days
Dexamethasone	40 mg**	Oral	Cycle 1: Day 1 ,8, ,15	Cycle 1: 21 days

Cycle 1 length = 21 days

* Starting dose will be determined as per the creatine clearance below (see 7.12)

**The dose of dexamethasone used can be determined by the treating physician and omitted if needed.

Cohort C and D Cycle 1

Treatment medication table. Patient may receive Lenalidomide + Dexamethasone OR Pomalidomide + Dexamethasone.

Agent	Dose Level	Route	Day	ReRx
Lenalidomide	25 mg*	Oral	Cycle 1: Day 1-14	Cycle 1: 21 days
Pomalidomide	4 mg	Oral	Cycle 1: Day 1-21	Cycle 1: 21 days
Dexamethasone	40 mg**	Oral	Cycle 1: Day 1 ,8, ,15	Cycle 1: 21 days

Cycle 1 length = 21 days

* Starting dose will be determined as per the creatinine clearance below (see 7.12)

** The dose of dexamethasone used can be determined by the treating physician and omitted if needed.

Cohort A and B Cycles 2-6

Treatment Medication Table. Patient may receive Lenalidomide based regimens.

Agent	Dose Level	Route	Day	Re Rx
Lenalidomide	25 mg*	Oral	Cycle 2-6: Day 1-21	Cycles 2-6: 28 days
Dexamethasone	40 mg**	Oral	Cycle 2-6: Day 1 ,8, ,15, 22	Cycles 2-6: 28 days

Note: Standard of care agents can be added for cycles 2-6 as long as the regimen contains lenalidomide

Cycles 2-6 length = 28 days

* Any dose-adjustments will be determined as per the creatine clearance below (see 7.12).

** The dose of dexamethasone used can be determined by the treating physician and omitted if needed.

Cohort C and D Cycles 2-6

Treatment medication table. Patient may receive Lenalidomide based regimen OR Pomalidomide based regimen.

Agent	Dose Level	Route	Day	ReRx
Lenalidomide	25 mg*	Oral	Cycles 2-6: Day 1-21	Cycles 2-6: 28 days
Pomalidomide	4 mg	Oral	Cycles 2-6: Day 1-21	Cycles 2-6: 28 days
Dexamethasone	40 mg**	Oral	Cycle 2-6: Day 1,8,15,22	Cycles 2-6: 28 days

Note: Standard of care agents can be added for cycles 2-6 as long as the regimen contains lenalidomide or pomalidomide

Cycles 2-6 length = 28 days

* Any dose-adjustments will be determined as per the creatinine clearance below (see 7.12).

** The dose of dexamethasone used can be determined by the treating physician and omitted if needed.

7.12

Creatinine Clearance (CrCl)	Lenalidomide Dose

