8.1 Lenalidomide Dose Modifications

Lenalidomide (Cycle 1: Day 1-14 Cycle 2-6: Day 1-21)	
Starting dose	25mg
-1	10 mg
-2	Discontinue

→ → Use the NCI Common Terminology Criteria for Adverse Events (CTCAE) version 5.0*
unless otherwise specified ← ←

CTCAE System/Organ/Class (SOC)	ADVERSE EVENT	AGENT	ACTION**
Investigations	Platelet count decreased Grade 4	Lenalidomide	
*Omit dose until AE has resolved to Grade 1 or better
 
 • Follow CBC weekly • If thrombocytopenia $<30,000/\text{mm}^3$ recurs, reduce dose by one dose level (by 5 mg) and continue therapy when platelet count $\geq 30,000/\text{mm}^3$ 
If, after lenalidomide has been omitted, and the AE does not return to \leqGrade 1 within 4 weeks, then the patient may continue on remaining agent(s) till the completion of maintenance and then proceed to off study

	Neutrophil count decreased Grade 4		
*Omit dose until AE has resolved to Grade 2 or better
 
 • Follow CBC weekly * If neutropenia has resolved to \leqGrade 2, resume dose at one level lower *If, after lenalidomide has been omitted, and the AE does not return to \leqGrade 2 within 4 weeks, then the patient may continue on remaining agent(s) till the completion of maintenance and then proceed to off study
Blood and lymphatic system disorders	Anemia Grade 4		
*Omit dose until AE has resolved to Grade 2 or better
 
 • Follow CBC weekly * If anemia has resolved to \leqGrade 2, resume dose at one level lower *If, after lenalidomide has been omitted, and the AE does not return to \leqGrade 1 within 4 weeks, then the patient may continue on remaining agent(s) till the completion of maintenance and then proceed to off study
	Febrile neutropenia \geq Grade 3		
 • Omit dose and follow CBC weekly • If neutropenia has resolved to \leqGrade 2, resume dose at same level with GCSF support (See Section 9.2)

CTCAE System/Organ/Class (SOC)	ADVERSE EVENT	AGENT	ACTION**
Cardiac disorders	Sinus bradycardia/ other cardiac arrhythmia Grade 2	Lenalidomide	Omit dose and follow at least weekly until resolution 
 • If AE resolves to \leqGrade 1, reduce dose by one dose level and continue therapy
	\geq Grade 3		
 • Discontinue study treatment and go off study

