8.4 Pomalidomide–Related Treatment Modification Guidelines for Adverse Events

8.41 Pomalidomide Dose Modifications

Pomalidomide (Cycle 1: Day 1-21 Cycle 2-6: Day 1-21)	
Dose Level	
Starting dose	4 mg
-1	3 mg
-2	2 mg
-3	1 mg
-4	Discontinue

→ → Use the NCI Common Terminology Criteria for Adverse Events (CTCAE) version 5.0*
unless otherwise specified ← ←

CTCAE System/Organ/Class (SOC)	ADVERSE EVENT	AGENT	ACTION**
Investigations	Neutrophil count decreased If ANC $<1.0 \times 10^9/L$ or ANC $>1.0 \times 10^9/L$ (up to LLN) with fever (temperature $>38.5^{\circ}C$)	Pomalidomide	Omit pomalidomide dose. Follow CBC weekly. If neutropenia has resolved to \leq Grade 2 prior to Day 21 and fever has resolved, restart pomalidomide at next lower dose level and continue through Day 21 of a 28-day cycle. If febrile neutropenia is the only toxicity for which a dose reduction is required, G-CSF may be used and the pomalidomide dose maintained.

CTCAE System/Organ/Class (SOC)	ADVERSE EVENT	AGENT	ACTION**
Investigations	Platelet count decreased If platelet count $<30 \times 10^9/L$	Pomalidomide	Omit pomalidomide dose Follow CBC weekly Hold anticoagulation/antiplatelet therapy until platelets $\geq 50,000/mm^3$ If platelet count resolves to \leq Grade 2 prior to Day 21, restart pomalidomide at next lower dose level and continue through Day 21 of each cycle
Skin and subcutaneous tissue disorders	Rash maculopapular Grade 2 or 3	Pomalidomide	Omit pomalidomide dose; follow weekly If the AE resolves to \leq Grade 1 prior to Day 21, restart pomalidomide at next lower dose level and continue through Day 21 of each cycle
	Grade 3-4 Stevens –Johnson Syndrome	Pomalidomide	Discontinue pomalidomide and remove patient from all study treatment
	\geq Grade 3 Erythema multiforme	Pomalidomide	Discontinue pomalidomide and remove patient from all study treatment
	Erythroderma \leq Grade 3	Pomalidomide	Omit pomalidomide dose; follow weekly If the AE resolves to \leq Grade 1 prior to Day 21, restart pomalidomide at next lower dose level and continue through Day 21 of the 28-day cycle
	Rash, maculo-papular Rash, acneiform Grade 4	Pomalidomide	Discontinue pomalidomide and remove patient from all study treatment
Nervous system disorders	Peripheral sensory neuropathy Grade 3	Pomalidomide	Omit pomalidomide dose and follow at least weekly. If the AE resolves to \leq Grade 1 prior to Day 21, restart pomalidomide at next lower dose level and continue through Day 21

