a) Absorption – oral absorption has been moderately rapid with first dose C_{max} occurring in 1.5 to 4 hrs. More than 70% of the pomalidomide dose is absorbed

in humans. A high fat meal decreased the rate of absorption but had minimal effect on overall extent of absorption; therefore drug may be administered without regard to food intake.

b) Distribution – Apparent volume of distribution in healthy subjects ranged from 74-138 L across a dose range of 1 to 10 mg daily.

Pomalidomide protein binding in human plasma is low to moderate (15.8% for R-enantiomer, 42.2% for S-enantiomer) and the binding is concentration independent in the concentration range of 30 and 1000 ng/mL. Drug distributes into semen.

c) Metabolism – Eight metabolites were detected in plasma, each at exposures < 10% of the plasma pomalidomide. CYP-dependent metabolites accounted for approximately 43% of the excreted radioactivity, while non-CYP dependent hydrolytic metabolites accounted for 25%, and excretion of unchanged pomalidomide accounted for 10%.

d) Excretion – In healthy patients, 72.8% of the dose was recovered in urine and 15.5% was recovered in feces. Less than 3% of the dose is excreted as unchanged pomalidomide in the urine. The geometric mean terminal elimination half-life ($t_{1/2}$) of pomalidomide was approximately 7.5 hours.

In pomalidomide renal studies, no dose adjustment was required for subjects with renal impairment. On hemodialysis days, subjects were instructed to take pomalidomide following hemodialysis. No dose adjustment of pomalidomide is required for patients with hepatic impairment as defined by the Child-Pugh criteria.

15.26 Potential Drug Interactions: Pomalidomide is partially metabolized by CYP1A2 and CYP3A4/5. Pomalidomide is also a substrate for P-glycoprotein (P-gp). Coadministration of pomalidomide with the strong CYP3A4/5 and P-gp inhibitor ketoconazole, or the strong CYP3A4/5 inducer carbamazepine, had no clinically relevant effect on exposure to pomalidomide. Coadministration of the strong CYP1A2 inhibitor fluvoxamine with pomalidomide increased mean exposure to pomalidomide by 125% compared to pomalidomide alone. If strong inhibitors of CYP1A2 are coadministered with pomalidomide, the pomalidomide dose should be reduced 50%.

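### In Cohorts C and D the post-cycle-1 specimens mix two drug-exposure states (pomalidomide to Day 21, lenalidomide to Day 14), and no biomarker analysis separates the drugs

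*Combined protocol and SAP*

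**What the plan says.** **Dosing.** For Cohorts C and D in cycle 1, Section 7.1 states: "Patient may receive Lenalidomide + Dexamethasone OR Pomalidomide + Dexamethasone". No allocation rule between the two is given. The lenalidomide row reads "Cycle 1: Day 1-14", the pomalidomide row "Cycle 1: Day 1-21", and the note below the table "Cycle 1 length = 21 days". The dose-modification tables agree: "Lenalidomide (Cycle 1: Day 1-14 Cycle 2-6: Day 1-21" in Section 8.1 and "Pomalidomide (Cycle 1: Day 1-21 Cycle 2-6: Day 1-21" in Section 8.41. Dexamethasone is on Days 1, 8 and 15 with either drug, and may be omitted.

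**Sampling.** Sections 4.0, 14.1, 14.3 and 14.4 place the second research marrow and blood draw before Day 1 of cycle 2 for all patients. The visit window is ±3 days, and no timing depends on the drug. Section 4.0 also schedules a patient medication diary.

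**Analysis.** Section 16.11 defines biomarker groups "by evaluating baseline and post treatment (after cycle one) biospecimens". Sections 16.2 and 16.311 estimate the response rate per biomarker within each cohort, with the cohorts kept separate. Evaluability requires both specimens. Sections 16.321 and 16.323 relate markers to response and to its depth by logistic regression and chi-square or exact tests. Section 14.3 screens plasma by untargeted mass spectrometry for features that separate responders from non-responders.

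**Handling of the drug.** Cohort is the only grouping factor (Section 5.1). The IMiD received is not a descriptive factor (Section 12.0), and Section 16 does not use it in any biomarker analysis.

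**The concern.** Two patients in the same cohort, sampled at the same visit, differ by a week in time since their last IMiD dose, and that difference is fixed by the drug they took. An untargeted screen is open to features that follow from this: parent drug, drug metabolites (Section 15.25 reports eight for pomalidomide in plasma), or short-lived metabolic and transcript changes.

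Nothing in the documents says the two drugs go to comparable patients. Cohort D has just relapsed on lenalidomide maintenance, and prior exposure in Cohort C may steer the choice. If response also differs by drug, a feature that only identifies the drug will separate responders from non-responders and could be reported as a response biomarker. Section 1.2 wants biomarkers that identify in advance who can be spared additional agents, and such a feature would be useless for that.

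**Working it through.** **1. The plan's sample size.** 2 × (30 + 2) + 2 × (60 + 3) = 64 + 126 = 190, as stated in Section 16.22. Evaluable: 2 × 30 + 2 × 60 = 180, of whom 120 are in Cohorts C and D. There is no power calculation to reproduce.

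**2. Days since last dose and residual drug.** Inputs: last cycle-1 dose on Day 14 (lenalidomide) or Day 21 (pomalidomide); cycle 2 Day 1 = Day 22; window ±3 days; half-lives from Section 15 of about 3 h for lenalidomide and, as a terminal value, "of pomalidomide was approximately 7.5 hours". Residual = 2^(−hours since last dose / half-life). The table assumes daily dosing and a draw just before the next dose would be due.

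| Draw day | Lenalidomide: days since dose / drug-free days | Pomalidomide: days since dose / drug-free days | Pomalidomide residual |
|---|---|---|---|
| 19 | 5 / 4 | 1 / 0 | 11% |
| 21 | 7 / 6 | 1 / 0 | 11% |
| 22 (nominal) | 8 / 7 | 1 / 0 | 2^(−24/7.5) = 11% |
| 23 | 9 / 8 | 2 / 1 | 1.2% |
| 25 | 11 / 10 | 4 / 3 | 2^(−96/7.5) = 0.01% |

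Lenalidomide at the nominal draw: 8 × 24 / 3 = 64 half-lives. At the earliest draw: 5 × 24 / 3 = 40 half-lives. Plasma drug is effectively zero in both cases. The difference in drug-free days is 4 at Day 19 and a constant 7 from Day 22 on. If a pomalidomide patient is drawn on a dosing day after the dose, the residual is 2^(−6/7.5) = 57% at 6 h and 2^(−12/7.5) = 33% at 12 h. Scheduled dexamethasone timing does not differ by IMiD.

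**3. What this can do to a marker-response association.** Take a marker that is positive only when pomalidomide was recently taken. Its apparent odds ratio for response equals the drug odds ratio:

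OR = [RR_pom / (1 − RR_pom)] / [RR_len / (1 − RR_len)].

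The one-cycle response rates are not in the documents, so the following are assumptions:

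| RR lenalidomide | RR pomalidomide | Apparent OR |
|---|---|---|
| 50% | 50% | 1.00 |
| 50% | 40% | 0.67 |
| 60% | 35% | 0.36 |
| 40% | 50% | 1.50 |

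The background figures give a rough range. Section 1.1 quotes 46–61% for lenalidomide in previously treated patients and 35–42% for pomalidomide 4 mg on 21 of 28 days. The extremes are (0.35/0.65)/(0.61/0.39) = 0.34 and (0.42/0.58)/(0.46/0.54) = 0.85. These are cross-study overall rates, not one-cycle rates. The same section quotes 47% and 63% from other pomalidomide studies, so even the direction is not settled.

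**4. Dependence on the drug split.** With pomalidomide share p in a cohort, mixing is proportional to p(1 − p): 0.25 at p = 0.5, 0.09 at p = 0.1, and zero at p = 0 or 1. The split is not stated.

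**5. Precision if markers are reported per drug.** The exact 95% interval half-width near a response rate of 50% is 13.2 points at n = 60, 18.7 at n = 30, 22.8 at n = 20 and 26.1 at n = 15. The per-drug sizes are assumptions.

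**The case against.** Much can be said against a stronger form of this point, and most of it stands.

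- **Clearance is not loss of effect.** A reader might infer that the lenalidomide specimens carry no drug effect at all. Section 15 gives elimination half-lives only. For dexamethasone the protocol itself lists a 4 h elimination half-life beside a 72 h metabolic effect. How long IMiD effects on any marker last cannot be determined from the documents.
- **The residual is modest.** The 33–57% figures need a draw 6–12 h after a dose. The nominal figure is about 11%, and it falls to 0.01% if cycle 2 starts three days late.
- **The extent is limited.** A reader might infer that the problem grows with the pomalidomide share, or that Cohorts C and D are merged. Mixing peaks at 50:50, and Section 16.31 analyses the cohorts separately. The 120 patients are a ceiling.
- **Part of the biomarker aim is untouched.** Baseline specimens do not carry this difference. Cohorts A and B receive only lenalidomide, and the first secondary goal concerns untreated patients. The response assessment does not depend on drug in the research specimen.
- **Bias is conditional.** If response does not differ by drug, the result is noise.
- **A diary already exists**, so some last-dose information may be available.
- **The main remedy is also the ordinary one** for combining two drugs in a cohort.

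What remains is enough to act on. Section 16.11 uses the post-cycle-1 specimens, the third secondary goal extends to previously treated patients, and Section 16.321 is not limited to Cohorts A and B. Nothing links the diary to the draw or to the analysis. Calling the study an estimation pilot does not prevent a drug marker from being estimated as a response marker.

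**Conclusion.** The point holds in limited form. Within Cohort C and within Cohort D, the post-cycle-1 specimens are drawn nominally one day after the last pomalidomide dose and eight days after the last lenalidomide dose, and the plan pools them with no IMiD term. A post-cycle-1 or change-from-baseline marker may therefore reflect only which drug was given.

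The size depends on two quantities the documents do not give: the drug split and the difference in one-cycle response between drugs. For a pure exposure marker, the assumed rates above give apparent odds ratios from 0.36 to 1.50, with 1.00 when the response rates are equal. Real markers may be affected less, or not at all.

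The documents do not support reading this as a flaw in the cohort response rates, in baseline markers, or in Cohorts A and B. Nor do they support a claim that biomarker effects have worn off in lenalidomide patients. No view is taken on either dosing schedule.

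**What to change.** Leave dosing and visits as they are.

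1. In Sections 16.11, 16.321 and 16.323, state that post-cycle-1 and change-from-baseline markers in Cohorts C and D are analysed stratified by, or adjusted for, cycle-1 IMiD. A marker that only identifies the drug has no variation within a drug stratum and drops out.
2. In Section 14.3, exclude parent-drug and drug-metabolite features from the untargeted panel before screening.
3. In Section 14.1, capture the time since the last IMiD and dexamethasone dose at each research draw, from the existing diary where it holds this and otherwise by one added field. Report its distribution by drug.

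No extra visit or specimen is needed. The cost is precision in per-drug estimates, as shown in step 5 of the working, and more so if the split is uneven. A stratified or adjusted estimate keeps both drugs in one analysis. The timing field is best added early, because last-dose times may be hard to reconstruct later.
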